Enhancing the Effects of Adolescent Alcohol Treatment with Atomoxetine

Funding Source: National Institute on Alcohol Abuse and Alcoholism (NIAAA)

National Institutes of Health

Division of Medications Development

[name]

Principal Investigator: [name], PhD, ABPP

Brown University

Center for Alcohol and Addiction Studies

[name] – US Postal Service [name] – Other

[contact] [contact]

E-mail: [name] [contact]

Medical Monitor: [name], PhD

Brown University Alpert Medical School

Chief of Mental Health and Behavioral Sciences & Associate Chief of

Staff for Education

Providence VA Medical Center

[contact]

Email: [contact]

Statement of Compliance

The study will be carried out in accordance with Good Clinical Practice (GCP) as required by the following:

- United States (US) Code of Federal Regulations (CFR) applicable to clinical studies (45 CRF Part 46, 21 CFR Part 50, 21 CFR Part 56 and 21 CFR Part 312)
- International Conference on Harmonisation (ICH) E6

All key personnel (all individuals responsible for the design and conduct of this study) have completed Human Subjects Protection Training.

Atomoxetine – Proof-of-Concept Trial

NCT#: NCT04565288

Protocol Synopsis

Name of Sponsor/Company: National Institute on Alcohol Abuse and Alcoholism (NIAAA)

Name of Investigational Product: Atomoxetine HCl, oral administration, 40mg to 80mg QD

Name of Active Ingredient: Atomoxetine

Protocol Number: ATOM-000

Study Title: Enhancing the Effects of Adolescent Alcohol Treatment with Atomoxetine

Principal Investigator: [name], PhD, ABPP

Study Centers: 1 site in the United States (Brown University)

Study Period: Estimated date first subject enrolled: 03/01/2021; Last completed: 03/31/2022

Phase of Development: 2

Primary Objectives

The first primary objective of this study is to evaluate the feasibility, acceptability, and tolerability of atomoxetine (40 mg/day for 3 days then 80 mg/day thereafter) as compared to placebo for 6 weeks plus a psychosocial platform comprised of motivational enhancement therapy and cognitive behavioral therapy (MET-CBT; "*Path 180*") among adolescents (ages 14 to 20 years) with alcohol use disorder as confirmed by the Diagnostic and Statistical Manual of Mental Disorders – Fifth Edition (DSM-5TM).

The second primary objective is to leverage a human laboratory paradigm (H-LAB) to evaluate the effects of atomoxetine on an intermediate phenotype (alcohol craving) associated with alcohol use and outcomes in clinical trials. We hypothesize that atomoxetine, as compared to placebo, will decrease the likelihood of craving in the human laboratory during *in vivo* alcohol cue reactivity.

Methodology

This proof-of-concept study is a double-blind, randomized, placebo-controlled, parallel group, single-site clinical trial. After obtaining consent/parent permission/assent, potential subjects and, if younger than 18 years, their parent(s) will complete a medical history and psychiatric diagnosis interview (about the adolescent) to screen for eligibility. Youth will also complete a physical examination, vital signs, drinking history by the timeline follow-back (TLFB) method, alcohol breathalyzer test, Clinical Institute Withdrawal Assessment for Alcohol-revised (CIWA-AR), prior/current medication use, urine toxicology screen, clinical chemistry, and the Columbia Suicide Severity Rating Scale (CSSR-S). Females of child-bearing potential will have a pregnancy test.

If eligible for the study, 50 subjects will be randomized in an approximate 1:1 ratio (targeting 21 subjects per group – 42 subjects total) to either atomoxetine or placebo for 6 weeks.

Atomoxetine will be dosed at 40 mg/day for three days then increased to the maintenance dose of 80 mg (active) taken orally once daily (QD) for an additional 5.5 weeks. Subjects randomized to the placebo condition will be given an equal number of visually matched capsules.

At the randomization/baseline visit and after 4 weeks of investigational product administration (i.e., Study Week 5), subjects will undergo a human laboratory paradigm (i.e., alcohol cue reactivity assessment).

Number of Subjects (Planned): 50 (targeting 21 subjects per group – 42 subjects total)

Main Inclusion/Exclusion Criteria: Subjects will be male and female adolescents, ages 14 to 20 years old, who meet DSM-5 criteria for alcohol use disorder. They must be seeking to reduce their alcohol use.

Investigational Product, Dosage and Mode of Administration: Dose titration and maintenance will occur as scheduled below. Atomoxetine will be self-administered by subjects once daily after eating and with a full glass of water beginning on Study Week 1, Day 1 and continuing through Study Week 6, Day 7. The first dose will be taken in the study clinic whenever possible. Subjects will be provided with water and a snack to take with first dose. Dose will be titrated, as tolerated, to a target dose of 80 mg once per day of atomoxetine. Capsules should be swallowed whole and should not be cut, crushed, or chewed. Capsules should be taken with food and water.

Schedule of Administration of Investigational Product

		AM Dose	PM Dose
Study Period	Time Period	(# of capsules)	(# of capsules)
Titration	Study Week 1, Day 1 – 3	40 mg (1)	None
Maintenance	Study Week 1, Day 4 – Week 6, Day 7	40 mg (2)	None

Reference Therapy, Dosage and Mode of Administration: Identically over encapsulated placebo tablets will be dispensed according to the same schedule as the atomoxetine capsules.

Table of Contents

Stateme	ent of Compliance	2
Regulat	ory History	3
Protoco	l Synopsis	3
	Abbreviations and Definition of Terms	
	ctory Statement	
1.1	Alcohol Use Disorder	
1.1	Human Laboratory Studies	
1.3	Rationale for Atomoxetine	
1.4	General Investigative Plan	
Study O	Objectives	14
2.1	Primary Objectives	
Study In	nterventions	
3.1	Investigational Products: Atomoxetine and Placebo	14
3.2	Investigational Product Acquisition	14
3.3	Investigational Product Storage and Stability	14
3.4	Investigational Product Dispensing	15
3.5	Investigational Product Accountability	
3.6	Investigational Product Administration	
3.7	Psychosocial/Behavioral Platform	
3.8	Concomitant Medications	17
Study P	rocedures	17
4.1	Recruitment of Subjects	17
4.2	Informed Consent, Assent, and Parent Permission	18
4.3	Selection and Withdrawal of Subjects	19
4.4	Eligibility Screening Assessments	21
4.5	Randomization/Baseline Visit(s) and Final Eligibility Assessments	
4.6	Measures Taken to Minimize/Avoid Bias	
4.7	Human Laboratory Paradigm Testing (H-LAB)	
4.8	Final Clinic Visit (End of Study Visit)	
4.9	Telephone Follow-up Assessments	
4.10	Conducting Sessions Remotely	26
	djustment Criteria	
5.1	Safety Criteria for Dose Adjustment or Stopping Doses	
5.2	Investigational Produce Dose Reduction	
5.3	Investigational Product Discontinuation	
5.4	Subject Withdrawal or Discontinuation Procedures	

SSRI	Selective serotonin reuptake inhibitors
THC	Tetrahydrocannabinol
TLFB	Timeline/follow-back interview
ULN	Upper limit of normal
US	United States
VAS	Visual Analog Scale
WHO	World Health Organization

8 28APR2025

Introductory Statement

1.1 Alcohol Use Disorder

Alcohol use disorder (AUD) affects nearly one-third of adults in the United States during their lifetime (1). Excessive alcohol use causes myriad acute and long-term medical, psychological, and social problems (2) and carries an economic burden of \$249 billion each year (3). Although advances in pharmacotherapy have improved treatment options for adults who struggle to reduce their alcohol use, treatment options for youth are limited.

Adolescent alcohol use is a leading public health concern. The harmful effects of underage drinking are irrefutable and include premature death and possible irreversible damage to the developing brain (4, 5). In addition, adolescence is a critical period in the pathogenesis of AUD; an estimated 3 to 15% of youth develops AUD before age 18 (6, 7). Clinical trials have tested psychosocial interventions with youth, including family treatments, cognitive behavior therapy (CBT), and motivational enhancement therapy (MET) that yield only modest short-term benefit (8-11). Our group has contributed substantially to this body of work (12-17).

One potential way to improve treatments is to augment psychosocial interventions with pharmacotherapy. The National Institute on Alcohol Abuse and Alcoholism (NIAAA) has mounted a concerted effort to identify medications that reduce drinking for nearly three decades. Although this effort improved treatment for adults, no medication is indicated for adolescent use and randomized controlled trials with teenagers are almost nonexistent. This gap raises key questions about if and how medications could benefit youth. Optimizing treatment options for youth requires closing this important gap, and FDA guidelines require that all applications for new pharmacotherapies include data from pediatric populations.

1.2 Human Laboratory Studies

Human laboratory studies of acute responses to alcohol, alcohol cues, or other experimental manipulations have progressed in important ways and hold potential to advance our understanding of how medications exert beneficial effects on drinking outcomes (18). These studies may help identify important individual difference factors affecting alcohol response, such as personality traits, drinking characteristics, and genotype, and aid in our understanding of the variability in cue and craving states, and provide additional information relevant to the design of clinical studies to assess the effectiveness of pharmacological agents.

The study to be conducted in this protocol utilizes an alcohol cue reactivity paradigm to attempt to recreate in the human laboratory risk conditions for relapse like those experienced by individuals with AUD in their natural environment. Alcohol cue reactivity, which involves systematic exposure to *in vivo* alcohol cues and simulates high-risk situations for relapse, is one of the most widely studied laboratory paradigms in the context of AUD (19, 20). Exposure to alcohol cues reliably elicits responses presumed to relate to the motivational processes that underlie drinking (21), and it is sensitive to medication effects among treatment seeking and non-treatment seeking adults and adolescents.

Impact on individual variability. Reactivity to alcohol and other drug cues varies from person to person, with some individuals showing little or no increase in target variables (e.g., craving) from the baseline or neutral cue trials to alcohol/drug cue trials (22-25). Some researchers have operationalized "responders" as individuals who show any change (22, 23, 26-28), whereas others have specified an exact minimum change (e.g., > 1-point increase in average craving) (25, 29, 30). Potential sources of variability include sex (31), genetic factors (32, 33), personality (26, 34), and substance use factors, such as lifetime alcohol

use indices and parental drinking problems (35), and these individual differences may moderate the effects of medications on alcohol cue reactivity (36-38).

Reproducibility. A highly cited meta-analysis of cue reactivity studies reported robust effects for self-reported craving in response to cues and a somewhat smaller, albeit still meaningful, effect size for physiological responses to cues (39). The autonomic profile of cue reactivity is fairly similar across drugs of abuse (40) and is often characterized by increases in heart rate and sweat gland activity and decreases in peripheral temperature. These physiological reactions are sensitive to medication effects (22, 41, 42).

Sensitivity to detect differences between experimental medication and placebo. The alcohol cue reactivity paradigm reliably detects significant medication-placebo differences for most, but not all, medications studied. Studies show that cue-induced craving is blunted by a variety of medications, such as naltrexone (22, 41, 43-47), gabapentin (48), mifepristone (49), prazosin (50), d-cycloserine (51), and olanzapine (52), as well as combinations of these medications (53). Some studies of these and other medications, however, did not find these effects (36, 54-56). Nonetheless, cue reactivity effects are generally consistent with decreases in craving observed in clinical trials of these medications (49, 57-61). It is noteworthy that certain medications that reduce drinking, namely topiramate and acamprosate, consistently fail to show medication-placebo differences in cue reactivity (62-65), and thus require other paradigms to characterize medication-placebo effects on clinically meaningful phenotypes.

Predictability of clinical trial success. Craving and other indices of cue reactivity are associated with relapse (66-68) and, as such, they are considered clinically relevant endophenotypes predictive of alcohol use outcomes (69). Craving is a strong predictor of drinking in the laboratory (46, 70, 71) and the natural environment (27, 54, 72-80), and medications (e.g., gabapentin, naltrexone) that decrease cue-elicited craving in the laboratory typically also reduce craving and drinking in clinical trials (43, 49, 58, 81). Indeed, human studies and animal models suggest that individuals for whom drug cues attain incentive motivational value or incentive salience are most likely to exhibit relapse (40, 82, 83). Although few studies have directly examined whether cue reactivity measured in the laboratory prospectively predicts clinical trial success, mounting evidence suggests it may be a powerful tool for understanding how interventions work and for identifying promising new treatment options for addiction (66, 84-91). Craving in response to alcohol or affective cues is predictive of subsequent drinking outcomes, including relapse (54, 75-80, 92); albeit others did not find this association. (93). Researchers have also examined the association between physiological cue reactivity and relapse and findings are mixed (94). Yet many studies show physiological reactivity (e.g., heart rate) predicts relapse (68, 77, 95-97).

1.3 Rationale for Atomoxetine

Atomoxetine is safe with adolescents and does not adversely interact with alcohol. It is a highly selective norepinephrine reuptake inhibitor that is FDA-approved to treat attention-deficit/hyperactivity disorder (ADHD) in children, adolescents, and adults. Unlike other ADHD pharmacotherapies, atomoxetine is not a stimulant and has no abuse potential (98-102). Pooled data from four trials showed it is equally well tolerated by heavy drinkers, non-heavy drinkers, and non-drinkers (103).

Atomoxetine targets brain mechanisms implicated in the pathogenesis of AUD, namely the norepinephrine system (104, 105). Norepinephrine innervates key limbic areas that govern arousal, reinforcement, and stress. Dysfunction in norepinephrine underlies problems with maintaining attentional homeostasis (106) and behavioral responses to stress (104, 107, 108), two key contributors to alcohol misuse. Although it does not appear to increase intracellular dopamine in regions involved in reward and reinforcement (e.g., nucleus accumbens), it increases extracellular dopamine in regions that drive craving and compulsive drug seeking (e.g., prefrontal cortex) (109).

There is strong preclinical evidence that altering the norepinephrine system reduces alcohol use and reinforcement. Selective pharmacological and neurotoxin-specific disruption of norepinephrine function reduces voluntary alcohol intake in rats (110, 111), and selective depletion of norepinephrine in the medial prefrontal cortex of high alcohol-consuming mice decreases alcohol consumption (112). Similarly, mice unable to synthesize norepinephrine because of dopamine-beta hydroxylase show reduced preference for alcohol (113). In addition, propranolol, a hypertensive and migraine medication that blocks the effects of norepinephrine on both β_1 - and β_2 -adrenergic receptors, suppresses progressive ratio operant alcohol-reinforced responding in alcohol-dependent and non-dependent rats (114). These findings further support the idea that manipulation of the norepinephrine system suppresses both the appetitive and consummatory reinforcing properties of alcohol.

These preclinical findings were supported by a rigorous double blind, placebo-controlled 12-week randomized controlled trial with 147 adults with comorbid AUD and ADHD (115). Individuals randomized to atomoxetine (mean dose = 90 ± 17.6 mg/day) had 26% fewer heavy drinking days compared to placebo. Reductions in ADHD symptoms were correlated with decreases in alcohol craving, and this association was more pronounced in the atomoxetine group (116). Two additional smaller and less scientifically rigorous studies also examined atomoxetine effects, including one with adolescents. In an open-label trial (N = 14) of adjunctive atomoxetine (41.9 ± 13.7 mg/day) to drug abuse treatment as usual, adult patients had longer durations of abstinence and reengaged in treatment more quickly following relapse when taking atomoxetine as compared to their past maximum period of abstinence (117). Patients also reported a significantly better quality of life and higher treatment efficacy scores after taking atomoxetine. There was no difference between patients with and without ADHD in terms of treatment responsiveness. Alcohol was the primary substance of abuse for 8 patients; the onset of dependence occurred on average during adolescence. In an additional trial, 70 adolescents, ages 13 to 19 years, with comorbid ADHD and substance use disorders were randomized to atomoxetine (weightadjusted up to 100 mg/day) or placebo plus psychotherapy for 12 weeks (118). Youth were not selected for a specific substance use disorder and thus varied in their type of substance use disorder (i.e., cannabis, nicotine, and alcohol use disorders). Although atomoxetine was well tolerated, substance use was a single aggregate outcome (no alcohol-specific outcomes reported; only 7 teens randomized to atomoxetine had AUD), and there was no effect of atomoxetine on ADHD symptoms or substance use.

Atomoxetine enhances executive function in patients with ADHD and healthy controls, especially in improving response inhibition (119) and researchers hypothesize that these effects may attenuate factors that confer liability for AUD and maintain pathological drinking habits (117). From this perspective, atomoxetine may not only affect drinking by blunting craving or altering the reinforcing properties of alcohol use, as observed in preclinical and clinical studies, but also by improving executive function. Attention, working memory, and decision-making are core facets of executive function and key to regulating behavior (120-122). Disruption of brain regions that govern executive function are strongly related to compulsive alcohol use and drug taking as well as problems associated with use (123, 124). Studies consistently show bidirectional relations of executive function and substance use, such that lower levels of executive function confers increased risk for developing addictions (125) and substance use produces acute (126) and long term (127) decreases in executive function. Indeed, impaired executive function is related to drinking in adults (128) and adolescents (129), and improved executive function via cognitive training is related to reduced alcohol use one-month post treatment, especially for those with strong automatic impulses to drink (130). Enhancing executive function may also improve outcomes of behavioral therapy by facilitating skill acquisition and durability of skill uptake.

Possible adverse effects of atomoxetine are considered mild given the dose (80 mg/day) and titration period proposed; participants randomized to atomoxetine will take one 40 mg capsule for the first 3 days, followed by one 80 mg capsule each day for the remainder of the active medication phase of the study. The FDA approved atomoxetine for treating children (ages 6 and older), adolescents, and adults with ADHD. As such, side effect data for atomoxetine comes from clinical trials research on children (ages 6 and older), adolescents, and adults with ADHD. The most common adverse reactions to atomoxetine, defined as \geq 5% and at least twice the incidence of placebo patients, in child and adolescent trails are nausea, vomiting, fatigue, decreased appetite, abdominal pain, and somnolence. In adult clinical trials, the most common adverse reactions are constipation, dry mouth, nausea, decreased appetite, dizziness, erectile dysfunction, and urinary hesitation.

As indicated by the FDA, pooled analyses of 12 short-term (6 to 18 weeks) placebo-controlled trials of atomoxetine with a total of 2,200 children and adolescents, including 11 trials for ADHD and 1 for enuresis, showed a greater risk of suicidal ideation early during treatment in those receiving atomoxetine compared to placebo. The average risk of suicidal ideation in patients receiving atomoxetine was 0.4% (N = 5/1357 patients), compared to none in the placebo condition (N = 851 patients). No suicides occurred in these trials. Notably, all suicidal ideation reactions in these trials occurred in children 12 and younger. We will be excluding youths younger than age 14 years. Studies with adults with ADHD or major depressive disorder have not revealed an increased risk of suicidal ideation among patients prescribed atomoxetine.

1.4 General Investigative Plan

This proof-of-concept study is a double-blind, randomized, placebo-controlled, parallel group, single-site clinical trial. After obtaining consent/parent permission/assent, potential subjects and, if younger than 18 years, their parent(s) will complete a medical history and psychiatric diagnosis interview (about the adolescent) to screen for eligibility. Youth will also complete a physical examination, vital signs, drinking history by the timeline follow-back (TLFB) method, alcohol breathalyzer test, Clinical Institute Withdrawal Assessment for Alcohol-revised (CIWA-AR), prior/current medication use, urine toxicology screen, clinical chemistry, and the Columbia Suicide Severity Rating Scale (CSSR-S). Females of child-bearing potential will have a pregnancy test.

If eligible for the study, 50 subjects will be randomized in an approximate 1:1 ratio (targeting 21 subjects per group – 42 subjects total who complete the protocol) to either atomoxetine or placebo for 6 weeks.

Atomoxetine will be dosed at 40 mg/day for three days then increased to the maintenance dose of 80 mg (active) taken orally once daily (QD) for an additional 5.5 weeks. Subjects randomized to the placebo condition will be given an equal number of visually matched capsules.

As shown in Figure 1, subjects will be seen in the clinic (or remotely) at the screening appointment, the randomization/baseline session, and at weekly visits during the study. At the randomization/baseline visit and after 4 weeks of investigational product administration (i.e., Study Week 5), subjects will undergo a human laboratory paradigm (i.e., alcohol cue reactivity assessment).

[figure not shown]

Figure 1: Overview of Study Chronology

Study Objectives

2.1 Primary Objectives

- Evaluate the feasibility, acceptability, and tolerability of atomoxetine (40 mg/day for 3 days then 80 mg/day thereafter) plus MET-CBT (i.e., "Path 180") for 6 weeks among adolescents with AUD as confirmed by the Diagnostic and Statistical Manual of Mental Disorders Fifth Edition (DSM-5TM).
- Apply our H-LAB paradigm to evaluate the effects of atomoxetine on intermediate phenotypes associated with alcohol use and outcomes in clinical trials. We hypothesize that atomoxetine, as compared to placebo, will reduce the likelihood of craving in the human laboratory during *in vivo* alcohol cue reactivity.

Study Interventions

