5.3 Investigational Product Discontinuation

Subjects who are discontinued from investigational product should continue in the study and complete all assessments, including the follow-up assessments, as well as *Path 180*. If the subject discontinues the investigational product before Study Week 5 then they will not complete the H-LAB paradigm.

- a. **Pregnancy.** Females who become pregnant during the medication phase of the study, Study Weeks 1 through 6, will be immediately discontinued from the investigational product. The investigator must report a pregnancy within 1 working day of the site being aware to the medical monitor.
- b. **Physical Illness.** Subjects will need to be removed from investigational products if they have a serious illness or a disabling condition that precludes them from taking the investigational product.

c. **Adverse Events.** If the subject experiences any AEs that are considered study drug related and for which the investigator has determined that continuation of the study drug could be detrimental to the health of the subject, then drug will be reduced for 1 week, then discontinued, or immediately discontinued as described above.

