6.1 Feasibility and Acceptability Endpoints

6.1.1 Primary Feasibility Endpoint

The number and percentage of subjects who completed the 6-week active medication phase will determine feasibility.

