8.1 Feasibility and Acceptability Endpoints

8.1.1 Primary Feasibility Endpoint

The number and percentage of subjects who completed the 6-week active medication phase will determine feasibility (target $\geq 70\%$).

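### Tolerability against placebo is part of the first primary objective but has no endpoint or by-arm analysis, and the 70% completion rule, undefined and not stated by arm, does not fill the gap

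*Combined protocol and SAP*

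**What the plan says.** The Synopsis sets the first primary objective as the "feasibility, acceptability, and tolerability of atomoxetine (40 mg/day for 3 days then 80 mg/day thereafter) as compared to placebo for 6 weeks", on top of the psychosocial platform. Section 2.1 restates the aim, to "Evaluate the feasibility, acceptability, and tolerability of atomoxetine", but leaves out the comparator.

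Section 6.1.1 gives the first endpoint: "The number and percentage of subjects who completed the 6-week active medication phase will determine feasibility". Section 8.1.1 repeats it with a target of at least 70%. Sections 6.1.2 and 8.1.2 set acceptability as at least 80% of subjects in the two satisfactory ranges of the CSQ-8. Sections 6.2 and 8.2 cover craving at Week 5. No other endpoint or analysis is given.

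Section 5.3 places pregnancy-related stopping within "the medication phase of the study, Study Weeks 1 through 6", which describes the phase in calendar terms. It also says: "Subjects who are discontinued from investigational product should continue in the study and complete all assessments".

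Safety information is gathered. Sections 7.1.3 and 7.1.4 have adverse events recorded and assessed for seriousness, severity and relationship to study drug. Section 7.1.6 records whether the drug was discontinued. Sections 3.5 and 4.6.5 provide for capsule counts. The heading of 7.1.3 mentions analysing safety endpoints, but its text contains no analysis.

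**The concern.** Of the three parts of the first primary objective, two have an endpoint and a threshold. The third, tolerability, has neither, and it is the part for which a placebo comparison is most informative. Followed as written, the plan produces no between-arm tolerability result.

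A reader might expect the completion figure to serve instead, since a badly tolerated drug should lower it. Whether it does depends on a definition that the plan does not give. If *completed* means still attending at Week 6, stopping the drug need not lower the figure at all. If it means still on drug, a single pooled percentage can still average a poor atomoxetine arm with a good placebo arm. Either way the 70% target could be met and the drug called feasible while many of those assigned to it had stopped taking it.

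**Working it through.** **Inputs from the plan.** 50 randomised, approximately 1:1, taken here as 25 per arm (Section 4.6.1); a target of 42 completing the protocol, 21 per group (Section 1.4); a completion target of at least 70% (Section 8.1.1). The plan states no denominator, discontinuation rate or attendance rate. The denominator of 50 and every rate below are assumptions.

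**Step 1: objective against endpoints.**

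| Part of the objective | Endpoint in Section 6 | Analysis in Section 8 | By arm? |
|---|---|---|---|
| Feasibility | Completion of the medication phase | Number and percentage, at least 70% | Not stated |
| Acceptability | CSQ-8 | Number and percentage, at least 80% | Not stated |
| Tolerability | None | None | None |

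**Step 2: threshold.** 0.70 × 50 = 35 completers.

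**Step 3: completion read as still in the study.** Take 42 of 50 still attending, borrowing the protocol's target as an attendance figure: 42/50 = 84%, a pass however many of the 42 have stopped capsules. If true attendance is 84%, the chance of reaching at least 35 of 50 is 99.6% (binomial tail). Counting only those on drug, the result changes once 8 of the 42 are off drug: (42 − 8)/50 = 34/50 = 68%, a fail. With 7 off drug it is 35/50 = 70%, still a pass.

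**Step 4: completion read as still on drug, arms pooled.** With 10/25 on atomoxetine and 25/25 on placebo, (10 + 25)/50 = 70%, a pass, although on-drug completion on atomoxetine is 10/25 = 40%. The same 70% applied to each arm would need 18 of 25 (0.70 × 25 = 17.5) and the atomoxetine arm would fail. If true on-drug completion were 50% on atomoxetine and 95% on placebo, the chance that the two binomial counts sum to at least 35 is 0.74.

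**Step 5: what a by-arm estimate would look like.** Assume 5/25 against 1/25 stopping for an adverse event, a difference of 0.20 − 0.04 = 0.16. The Wilson limits are [p + z²/2n ± z√(p(1 − p)/n + z²/4n²)] / (1 + z²/n). With z = 1.96 and n = 25 they are 0.0886 to 0.3913 for 5/25, and 0.0071 to 0.1954 for 1/25. The Newcombe limits are:

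- lower: 0.16 − √[(0.20 − 0.0886)² + (0.1954 − 0.04)²] = 0.16 − 0.191 = −0.031
- upper: 0.16 + √[(0.3913 − 0.20)² + (0.04 − 0.0071)²] = 0.16 + 0.194 = 0.354

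That is 16 points, 95% CI −3 to 35.

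**The case against.** **The data exist and are watched.** Adverse events are graded, discontinuation is recorded, the medical monitor tracks trends, and the DSMB reviews cumulative adverse event data. This stands in part. A reader might infer that the tolerability objective cannot be answered at all, and the documents do not support that: what is missing is a prespecified endpoint and comparison. But review by a Board that is blinded to assignment unless it asks otherwise is monitoring, not the analysis of a primary objective.

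**Completing a medication phase naturally means taking the medication.** The plan uses other words for finishing the protocol (Section 1.4), and Section 5.3 separates stopping the drug from leaving the study. This is a fair reading. A reader might infer that the plan does count subjects who are off drug as completers; the documents do not settle that. Because Section 5.3 also gives the phase as study weeks and keeps stoppers in follow-up, the most that can be said is that they can be counted. Step 4 shows that the on-drug reading does not cure the problem while the rule stays pooled.

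**The scenarios are invented.** True, and they show only what the rule permits. Using the target of 42 as an attendance figure is also loose: a subject who stops before Week 5 does not do the second laboratory session and may not count as having completed the protocol.

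**The trial is too small for a tolerability comparison.** It is too small for a useful test, as Step 5 indicates. That is a reason to estimate and show the interval, not to leave the comparison out.

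**Conclusion.** The point holds in two parts. First, tolerability relative to placebo is named in the first primary objective, yet Sections 6 and 8 contain no endpoint or between-arm analysis for it. This rests on the text alone and needs no assumption. Second, the completion rule does not fill the gap, because completion and its denominator are undefined and the rule is not stated by arm. Under the assumed denominator of 50, it can pass at 84% on attendance with 8 of the 42 attenders off drug (68% on drug), or at exactly 70% with only 40% of the atomoxetine arm on drug.

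A reader might infer that atomoxetine is poorly tolerated here, or that the rule would pass whatever happened. The documents give no observed rates, and under a by-arm, on-drug definition the same rule would catch the second case. The change should be made; it concerns what is prespecified and reported, and takes no position on the dosing or stopping rules.

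**What to change.** - **Objective.** Align the Synopsis and Section 2.1 on whether placebo is the comparator.
- **Tolerability, in 6.1 and 8.1.** Among randomised subjects dispensed study drug (Section 4.6.1 treats those never dispensed it as randomisation failures and replaces them), report by arm the proportion stopping study drug because of an adverse event by Week 6, with the difference and a 95% Newcombe interval. Report the proportion with any dose reduction separately, because Section 5.2 allows a later return to the target dose. Add adverse events by severity and relatedness, by arm.
- **Completion.** State the denominator. Report by arm both on-drug completion, with a stated window around the final visit (which Section 4.8 places only typically at Week 6, Day 7), and visit attendance.
- **Status.** The document carries a date of 28APR2025, the Synopsis estimates last completion at 03/31/2022, and Sections 6.2 and 8.2 describe ratings and the craving comparison in the past tense. This does not prove that data have been analysed. If they have been seen, label the additions supplementary and do not redefine the primary endpoint.

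**Cost.** A few small tables, mostly from data already collected. Dose reductions may have to come from dosing records, since Section 7.1.6 names only discontinuation. The intervals will be wide, and the feasibility figure may look less favourable.
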